# **Study Stopping Rules for Entire Study**

During a hypoglycemic or hyperglycemic challenge, if a subject experiences DKA, severe hypoglycemia with seizures or severe hypoglycemia requiring glucagon, the following actions will be taken:

- 1. Site will notify the sponsor within approximately 24 hours of receiving knowledge of the event.
- 2. Sponsor will notify Food and Drug Administration (FDA) within approximately 72 hours of knowledge of the event.
- 3. The Clinical Events Committee (CEC) will review the event within 10 days from the time that the sponsor is notified and provide one of the following recommendations:
  - enrollment and study procedures may continue
  - stop enrollment, previously enrolled subjects are still allowed to continue in study
  - stop entire study, withdraw previously enrolled subjects

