#### **Hypoglycemic Treatment Guidelines**

The following are specific hypoglycemic treatment guidelines during the challenges:

Subjects who have glucose less than (<) 70 mg/dL (3.9 mmol/L) and accompanied by seizure, loss of consciousness, or altered mental status (i.e., uncooperative with food or liquid orally so that subject is unable to take carbohydrate to raise glucose) will no longer be allowed to continue in challenges (stop the challenge and DO NOT continue with any future challenges) and the following should be considered:

- Dextrose: 25 grams of dextrose using an ampule (50 ml/25 grams of dextrose) of Dextrose 50% IV push over 3 minutes. Repeat administration may be given again after 15 minutes if glucose is not above 100 mg/dL (5.6 mmol/L). This dose may be adjusted according to investigator discretion based on subject age and other clinical considerations.
- Glucagon emergency kit (glucagon for injection [ribosomal DNA origin] 1 mg, with 1 mL of diluting solution administered intramuscular): may be given if Dextrose was not able to be given due to IV access or per investigator discretion.

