#### 20.1.3. Study Stopping Rules

During a hypoglycemic or hyperglycemic challenge, if a subject experiences DKA, severe hypoglycemia with seizures or severe hypoglycemia requiring glucagon, the following actions will be taken:

- 1. Site will notify the sponsor within approximately 24 hours of receiving knowledge of the event.
- 2. Sponsor will notify Food and Drug Administration (FDA) within approximately 72 hours of knowledge of the event.
- 3. The Clinical Events Committee (CEC) will review the event within 10 days from the time that the sponsor is notified and provide one of the following recommendations:
  - enrollment and study procedures may continue
  - stop enrollment, previously enrolled subjects are still allowed to continue in study
  - stop entire study, withdraw previously enrolled subjects

10976639DOC Version D Page 117 of 170

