
 
Risks with drawing blood may include:
 
Discomfort and bruising
 
Insertion of an IV catheter and drawing blood may also result in faintness, inflammation of the blood vessel, pain and bruising at the needle site
 
There is also a slight possibility of infection.
 
	Prevention and mitigation include:
Risks with IV Saline Infusion	Prevention and Mitigation
Risks with saline infusion may include:	Prevention and mitigation include:  Qualified investigator will be present during experiment  Constant observation and monitoring of the subject during FST(s)  Treatment of these risks include:  Reduction of IV fluid if subject shows signs of congestive heart failure (CHF), lower extremity edema, crackles on lung auscultation or S3 heart sound  Subjects who still exhibit signs of fluid overload at time of discharge will be transported to the emergency room (ER) or follow guidelines of the local institution for the disposition of subject.
Risks with hyperglycemic challenges	Prevention and Mitigation
Risks with hyperglycemia may include:  Diabetic ketoacidosis Symptomatic ketosis Cardiovascular event Dehydration Potassium and sodium imbalance Shock Altered mental status Coma Acidosis	Prevention and Mitigation include:     Follow frequent blood sampling per protocol (See Section 10.2.1.6.4.1 and 11.2.1.6.2.1)     Clear guidelines for management during hyperglycemic challenge     IV access to give immediate insulin     Qualified investigator will be present during experiment     Stopping challenge procedures if ketones are elevated or subject is exhibiting signs and

10976639DOC Version D Page 120 of 170 Medtronic

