	symptoms of DKA (Please refer to the ketone management guidelines in the protocol)  Limiting the time the subject is allowed to stay in the hyperglycemic ranges  The subject is under constant observation and monitoring at all times during the challenges  Preventing subjects who do not have a carb/insulin ratio and insulin sensitivity factor from participating in the challenge (observational only)  Investigational centers are to use glucose meter in the event a FST blood glucose value is not available at the required time interval.  Follow the Ketone management instructions per protocol  Treatment of these risks include:  IV fluid administration with normal saline (NS) will be per investigator's discretion  IV insulin administration will be per investigator's discretion  Transfer to ER or follow DKA guidelines of the local institution for the disposition of subject if subject is exhibiting signs and symptoms of DKA
Risks with hypoglycemic challenges Risks for hypoglycemia may include:	Prevention and Mitigation Prevention and Mitigation include:

 
Seizure
 
Coma
 
Altered mental status
 
Loss of consciousness
 
Cardiovascular event
 
Death
 
Risk of rebound hyperglycemia with ketosis
 
	
 
Follow frequent blood sampling per protocol (See Section 10.2.1.6.4.1 and 11.2.1.6.2.1)
 
Clear guidelines for management during hypoglycemic challenge IV access to give immediate dextrose or other emergency drugs
 
Qualified investigator will be present during experiment.
 
Limiting the time the subject is allowed to stay in the hypoglycemic ranges
 
The subject is under constant observation and monitoring at all times during the challenges
 
Preventing subjects who do not have a carb/insulin ratio and insulin sensitivity factor from participating in the challenge (observational only)
 
Investigational centers are to use glucose meter in the event a YSI blood glucose value is not available at the required time interval.
 

10976639DOC Version D Page 121 of 170

Risks with exercise:	Treatment of these risks include:  IV administration of dextrose per investigator's discretion  Glucagon per investigator's discretion  Transfer to ER or follow severe hypoglycemia guidelines of the local institution for the disposition of subject.  Prevention and Mitigation

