#### 21.5. Risk Determination

#### **US only:**

In the opinion of the sponsor, this study is considered to be a significant risk (SR) study. Results of an evaluation of the requirements per 21 CFR Part 812.3, led to the SR determination as follows:

Although the devices used in the study do not present any significant risk to subjects, the study will involve hypoglycemic and hyperglycemic challenges that presents a potential serious risk to subjects.

Therefore, submission of an Investigational Device Exemption (IDE) application to the United States FDA is required (due to the risk associated with testing performed during the study).

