#### 22.1. Definitions and Classification of Adverse Events

Medtronic uses the definitions provided in NMPA (former CFDA) Order No. 25, ISO 14155:2011 and 21 CFR 812 for AE definitions. ISO14155:2011 definitions are used for AE classifications while expedited reporting to local authorities/EC should be done based on local definitions of local regulations. Where the definition indicates "device", it refers to any device used in the study. This might be the device under investigation, or any market released component of the system. Medtronic follows MEDDEV 2.7/3 revision 3 guidelines for classifying causality levels; but will apply these causality definitions across all events, not only serious adverse events and definitions have been adapted accordingly.

**Severe Hypoglycemia** is an event requiring assistance of another person due to altered consciousness to actively administer carbohydrate, glucagon, or other resuscitative actions. This means that the subject was impaired cognitively to the point that he/she was unable to treat himself or herself, was unable to verbalize his or her needs, and was incoherent, disoriented and/or combative.

These episodes may be associated with sufficient neuroglycopenia to induce seizure or coma. Plasma glucose measurements may not be available during such an event, but neurological recovery attributable to the restoration of plasma glucose to normal is considered sufficient evidence that the event was induced by a low plasma glucose concentration. (Adapted from American Diabetes Association Workgroup on Hypoglycemia, Diabetes Care 28:1245-1249, 2005)

**Diabetic Ketoacidosis/DKA** diagnostic criteria: blood glucose greater than (>) 250 mg/dL or greater than (>) 13.9 mmol/L, arterial pH less than (<) 7.3, bicarbonate less than (<)15mEq/L, moderate ketonuria or ketonemia and requiring treatment within a health care facility. (**American Diabetes Association-Diabetes Care, Volume 27, Supplement 1, January 2004; S94-S102**)

Hyperglycemic events will be recorded as DKA if the event includes the presence of all of the following:

- Arterial blood pH less than (<) 7.30 or serum bicarbonate less than (<) 15 mEg/L

- Blood glucose greater than (>) 250 mg/dL or greater than (>) 13.9 mmol/L
- Serum ketones or large/moderate urine ketones
- Symptoms such as polyuria, polydipsia, nausea, or vomiting
- Treatment provided in a health care facility

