#### 23. Data Review Committees

#### 23.1. Clinical Events Committee

A clinical events committee (CEC) consisting of external physicians with an expertise in endocrinology and the management of diabetes including insulin pumps and CGM will be convened. The CEC will review AEs as required per protocol, which include reports of:

- Serious Adverse Event
- Serious Adverse Device Effect
- Unanticipated Adverse Device Effect
- Severe Hypoglycemia
- Diabetic Ketoacidosis

During a hypoglycemic or hyperglycemic challenge, if a subject experiences DKA, severe hypoglycemia with seizures or severe hypoglycemia requiring glucagon, the following actions will be taken:

- 1. Site will notify the sponsor within approximately 24 hours of receiving knowledge of the event.
- 2. Sponsor will notify Food and Drug Administration (FDA) within approximately 72 hours of knowledge of the event.
- 3. The Clinical Events Committee (CEC) will review the event within 10 days from the time that the sponsor is notified and provide one of the following recommendations:
  - enrollment and study procedures may continue
  - stop enrollment, previously enrolled subjects are still allowed to continue in study
  - stop entire study, withdraw previously enrolled subjects

The CEC will assess events to determine agreement or disagreement with the investigator classification of an event. The CEC will only provide three causality assessments for device and procedure relatedness: Not Related, Possible, and Causal relationship.

Causality Categories for Investigational Center	Causality Categories for CEC:
Not Related	
 
Not Related
 

 
Unlikely
 
	
 
Possible
 

 
Possible
 
	
 
Causal relationship
 

Probable	
Causal relationship	

The sponsor will notify the investigator of any disagreement in assessment of an event by the CEC.

10976639DOC Version D

Page 134 of 170

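### A challenge death or serious cardiovascular event without DKA, seizure or glucagon use requires no dated continue/stop recommendation from the Clinical Events Committee

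*Protocol*

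**What the plan says.** The rule for the whole study appears in the synopsis (Study Stopping Rules for Entire Study), in Section 20.1.3 and in Section 23.1, with the same triggers each time. It is limited to events during a challenge: "if a subject experiences DKA, severe hypoglycemia with seizures or severe hypoglycemia requiring glucagon, the following actions will be taken". A trigger starts three dated steps. The site tells the sponsor in about 24 hours. The sponsor tells FDA in about 72 hours. The CEC reviews the event within 10 days of sponsor notification and gives one of three recommendations: carry on, close enrollment while enrolled subjects continue, or stop and withdraw everyone.

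Section 23.1 also gives the CEC a general task. It reviews all SAEs, serious and unanticipated device effects, severe hypoglycemia and DKA. The output stated for that review is: "The CEC will assess events to determine agreement or disagreement with the investigator classification of an event". The committee also assigns one of three causality categories. No deadline is given.

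Section 21.1 lists the expected harms. The hypoglycemic list ends with "Cardiovascular event Death Risk of rebound hyperglycemia with ketosis". The hyperglycemic list reads "Diabetic ketoacidosis Symptomatic ketosis Cardiovascular event Dehydration Potassium and sodium imbalance Shock Altered mental status Coma Acidosis". Section 21.5 rests the sponsor's significant-risk determination on the challenges rather than the device: "the study will involve hypoglycemic and hyperglycemic challenges that presents a potential serious risk to subjects".

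**The concern.** The triggers cover DKA and two forms of severe hypoglycemia. They do not include the gravest harm that Section 21.1 names for the hypoglycemic challenge, or the cardiovascular harm it names for both challenges. After a challenge death, the pressing safety question is whether the remaining subjects should continue with the study and its challenges. The schedule for ages 14 to 80 has two hypoglycemic and two hyperglycemic challenges per subject; they are at local discretion in China and limited everywhere to subjects with known insulin ratios. If the rule is followed exactly, the committee must answer within 10 days after a seizure with severe hypoglycemia, yet need not answer at all after a death. Nothing in the protocol or SAP explains that ordering.

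**Working it through.** No arithmetic applies and there is no figure to reproduce. The check is to test each event against the trigger wording, and then to see whether any other route supplies what is missing.

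**Step 1. Test against the trigger.**

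- Severe hypoglycemia with a seizure in a challenge, subject recovers: triggers the rule.
- Death in a challenge, with no DKA, no seizure with severe hypoglycemia and no glucagon given for severe hypoglycemia: no trigger.
- Serious cardiovascular event in either challenge, same conditions: no trigger.

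**Step 2. Where the untriggered events go.** A death is an SAE under Section 22.1, and so is a cardiovascular event that meets the seriousness criteria there. Both are reported under Section 22.3 and fall in the CEC's general review under Section 23.1. That review has no date. Its stated output is the classification view quoted above. Section 23.1 does not bar the committee from further advice, but it requires none.

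**Step 3. Look for another route to a dated committee view.**

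| Route | What it provides | Dated, required continue/stop view from the CEC? |
|---|---|---|
| Section 22.3 | Sponsor told, desired within 24 hours | No; reporting only |
| Section 22.4 (US) | Unanticipated device effects reported within 10 working days | No; the definition concerns device-associated effects, mainly ones not identified beforehand, while these harms are listed and arise from the procedure |
| Table 3 (China) | SAE to sponsor at once and to local authorities within 24 hours; a comment on continuing goes to the ethics committee | No; the comment does not come from the CEC, and no deadline for it can be read in the broken table text |
| Sections 10.2.1.6.4.4 and 20.1.1 | Stop a challenge for chest pain, shortness of breath or other safety symptoms; bar a subject from later challenges after listed events | No; subject level |
| Section 26.1 | Continuing ethics review | No |
| Section 27.2.3 | Sponsor or IRB/EC may disqualify a center | No; discretionary and center level |
| Section 27.10 | Sponsor may revisit the protocol on CEC input | No; discretionary |
| Section 27.13 | Sponsor or regulator may suspend the study | No; discretionary |
| Section 27.13.1 | Investigators must reassess once risks outweigh benefits | No; center level and undated |

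Section 23 names no other committee. The SAP adds nothing: Section 7.8 has no interim analysis, and the China-only text in Section 7.2 says there are no statistical grounds for termination.

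**Result.** For a challenge death or serious cardiovascular event outside the three triggers, no provision in either document requires a dated continue/stop recommendation from the committee.

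**The case against.** The strongest reply is that the gap is narrow and the gain modest. These events reach the sponsor quickly and do reach the CEC. A sponsor or regulator can suspend the study at any time, and most would act after a death. Section 20.1.3 itself yields only a recommendation, with no pause during the 10 days, and none of its three options halts challenges alone. Exclusion criteria 10 to 12 remove subjects with seizure disorders, syncope and cardiovascular history, and Section 15 requires a qualified provider throughout. Section 26.2 also binds investigators to conditions set by the IRB/EC and regulators; those are not in these documents and might add escalation steps.

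All of this stands as a limit on the benefit. None of it explains why a seizure with severe hypoglycemia requires a dated committee view and a death may not.

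A reader might infer three stronger claims that the documents do not support.

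- *That these events go unreported or unreviewed.* Sections 22.3 and 23.1 show otherwise.
- *That severe hypoglycemia treated with IV dextrose is an equal defect.* The argument is tempting. The Section 22.1 definition covers help "to actively administer carbohydrate, glucagon, or other resuscitative actions", whereas the trigger turns on glucagon, which in a challenge "may be given if Dextrose was not able to be given due to IV access or per investigator discretion". But the low is induced on purpose, a provider is available, and the subject is barred from further challenges. Reserving study-level review for seizure or glucagon use is a reasonable severity cut.
- *That most harms listed in Section 21.1 are left uncovered because few are named as triggers.* The labels overlap: coma and altered mental status can be presentations of severe hypoglycemia, and acidosis overlaps with DKA. Others, such as dehydration, need not be triggers at all.

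**Conclusion.** The point holds for death and serious cardiovascular events in a challenge that occur without DKA, without severe hypoglycemia with seizure, and without severe hypoglycemia needing glucagon. What is missing is specific: a deadline for the CEC's review and a required recommendation on whether to continue. It is a patient-safety weakness that should be corrected, not evidence that the study lacks oversight. A reader might infer that the study would run on unchecked after a death; the discretionary suspension powers and the reporting duties mean that the documents do not say that.

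The textual reading is firm, because the same triggers stand in all three places. The conclusion assumes that no escalation duty sits in approval conditions outside these documents. Frequency is left open because no event rates are given.

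**What to change.** In the synopsis, Section 20.1.3 and Section 23.1, keep the three triggers and add: *any death, and any other SAE (including a serious cardiovascular event), with onset during a challenge or judged by the investigator or sponsor at least possibly related to the challenge procedure.* Make this a separate clause, so that the opening limit to events during a challenge does not cut it short. A death after discharge that follows an event begun in the challenge is then included. The 10-day clock should start at sponsor notification and should not wait for the CEC's own causality assessment.

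Extending the trigger to all severe hypoglycemia treated with dextrose is optional for the sponsor. An episode that meets the SAE definition in its own right would already come in under the added wording. Treatment guidance and subject-level stopping rules need no change.

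The cost is a protocol amendment with IRB/EC approval and, where applicable, regulatory approval (Section 27.10), across up to 22 centers. Each added event also needs an FDA notice in about 72 hours and a CEC recommendation within 10 days; the documents do not allow that number to be estimated. The committee, the SAE reporting route and the causality categories already exist. The rule would still produce a recommendation, not an automatic pause.

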### 21. Risks and Benefits

#### 21.1. Potential Risks

Risk with Sensors	Prevention and Mitigation
Risks with Sensors may include:	Prevention and mitigation include:

 
Skin irritation or reaction to adhesives
 
Bruising
 
Discomfort
 
Redness
 
Bleeding
 
Excessive bleeding due to anticoagulants
 
Pain
 
Rash
 
Infection
 
Irritation from tapes used with glucosesensing products
 
Raised bump
 
Appearance of a small "freckle-like" dot where needle was inserted
 
Allergic reaction
 
Syncopal episode secondary to needle insertion
 
Soreness or tenderness
 
Swelling at insertion site
 
Sensor fracture, breakage or damage
 
Minimal blood splatter associated with sensor needle removal
 
Residual redness associated with adhesive and or tapes
 
	Prevention and Mitigation Prevention and mitigation include:  • Follow the provided user guides for insertions and care of sensors.  • If a sensor site becomes infected or inflamed, the sensor will be removed and another placed in a new location

 
Scarring
 
Scab
 
Blister
 
Itchiness
 
Inflammation
 
Anxiety
 
Anxiety associated with insertion
 
	
Risks with Transmitter	Provention and Mitigation
	Prevention and Mitigation
Risks with Transmitter may include:	Prevention and mitigation include:

 
Skin irritation or reaction to adhesives
 
Bruising
 
Discomfort
 
Redness
 
Pain
 
	
 
Follow the provided user guides.
 
Train on the proper use of the transmitters.
 

10976639DOC Version D Page 118 of 170 Medtronic

DI	

Rash

Infection

	
Irritation from tapes used with glucose-	
sensing products	
Raised bump	
Allergic reaction	
Soreness or tenderness	
Residual redness associated with adhesive	
and/ or tapes	

 
Scarring
 
	
Scab	
Blister     Halding and a second	
Itchiness     Inflammation	
Inflammation  Risks with Inserter	Prevention and Mitigation
Risks with inserters may include:	Prevention and mitigation include:
-	Follow the provided user guides for insertions
Improper insertion may lead to device	and care of device.
performance issue	Train on the proper use of the inserter and skin
	preparation prior to insertion.
Risks with Finger Sticks	Prevention and Mitigation
Risks with frequent finger stick testing may include:	Prevention and mitigation include:
Potential risks associated with frequent	Follow the provided user guides for use of the
meter testing of blood glucose and blood	study meter with fingerstick testing.
ketones include discomfort and ecchymosis. I	
 
I rain on the proper use of the meter and
 

ketones include discomfort and ecchymosis	Train on the proper use of the meter and fingerstick testing.
at tips of fingers	fingerstick testing.

at tips of fingers

Potential risks associated with finger stick

	···

 
at tips of fingers
 
Potential risks associated with finger stick testing include discomfort and bruising
 
	fingerstick testing.
at tips of fingers  • Potential risks associated with finger stick	···
at tips of fingers  • Potential risks associated with finger stick testing include discomfort and bruising  Risks with IV Catheter Insertion	fingerstick testing.  Prevention and Mitigation
at tips of fingers  • Potential risks associated with finger stick testing include discomfort and bruising  Risks with IV Catheter Insertion  Risks with IV catheter insertion may include:	Prevention and Mitigation  Prevention and mitigation include:
at tips of fingers  • Potential risks associated with finger stick testing include discomfort and bruising  Risks with IV Catheter Insertion  Risks with IV catheter insertion may include:  • Pain	Frevention and Mitigation  Prevention and mitigation include:  • Qualified individual to perform IV catheter
at tips of fingers  • Potential risks associated with finger stick testing include discomfort and bruising  Risks with IV Catheter Insertion  Risks with IV catheter insertion may include:  • Pain  • Bruising	Prevention and Mitigation  Prevention and mitigation include:  • Qualified individual to perform IV catheter insertion
at tips of fingers  • Potential risks associated with finger stick testing include discomfort and bruising  Risks with IV Catheter Insertion  Risks with IV catheter insertion may include:  • Pain  • Bruising  • Infection	Prevention and Mitigation  Prevention and mitigation include:  • Qualified individual to perform IV catheter insertion  • Constant observation and monitoring of the
at tips of fingers  Potential risks associated with finger stick testing include discomfort and bruising  Risks with IV Catheter Insertion  Risks with IV catheter insertion may include:  Pain Bruising Infection Irritation	Prevention and Mitigation  Prevention and mitigation include:  • Qualified individual to perform IV catheter insertion  • Constant observation and monitoring of the subject during FST(s)
at tips of fingers  Potential risks associated with finger stick testing include discomfort and bruising  Risks with IV Catheter Insertion  Risks with IV catheter insertion may include:  Pain Bruising Infection Irritation Syncopal episode secondary to catheter	Prevention and Mitigation  Prevention and mitigation include:  • Qualified individual to perform IV catheter insertion  • Constant observation and monitoring of the
at tips of fingers  Potential risks associated with finger stick testing include discomfort and bruising  Risks with IV Catheter Insertion  Risks with IV catheter insertion may include:  Pain Bruising Infection Irritation	Prevention and Mitigation  Prevention and mitigation include:  • Qualified individual to perform IV catheter insertion  • Constant observation and monitoring of the subject during FST(s)  • Sterile technique will be used to insert the IV
at tips of fingers  Potential risks associated with finger stick testing include discomfort and bruising  Risks with IV Catheter Insertion  Risks with IV catheter insertion may include:  Pain Bruising Infection Irritation Syncopal episode secondary to catheter insertion Swelling.	Prevention and Mitigation  Prevention and mitigation include:  • Qualified individual to perform IV catheter insertion  • Constant observation and monitoring of the subject during FST(s)  • Sterile technique will be used to insert the IV  Treatment of these risks include:
at tips of fingers Potential risks associated with finger stick testing include discomfort and bruising  Risks with IV Catheter Insertion  Risks with IV catheter insertion may include: Pain Bruising Infection Irritation Syncopal episode secondary to catheter insertion Swelling. Discomfort	Prevention and Mitigation  Prevention and mitigation include:  • Qualified individual to perform IV catheter insertion  • Constant observation and monitoring of the subject during FST(s)  • Sterile technique will be used to insert the IV  Treatment of these risks include:  • Removal of IV catheter if subject experiences
at tips of fingers  Potential risks associated with finger stick testing include discomfort and bruising  Risks with IV Catheter Insertion  Risks with IV catheter insertion may include:  Pain Bruising Infection Irritation Syncopal episode secondary to catheter insertion Swelling.	Prevention and Mitigation  Prevention and mitigation include:  • Qualified individual to perform IV catheter insertion  • Constant observation and monitoring of the subject during FST(s)  • Sterile technique will be used to insert the IV  Treatment of these risks include:  • Removal of IV catheter if subject experiences significant discomfort
at tips of fingers Potential risks associated with finger stick testing include discomfort and bruising  Risks with IV Catheter Insertion  Risks with IV catheter insertion may include: Pain Bruising Infection Irritation Syncopal episode secondary to catheter insertion Swelling. Discomfort	Prevention and Mitigation  Prevention and mitigation include:  • Qualified individual to perform IV catheter insertion  • Constant observation and monitoring of the subject during FST(s)  • Sterile technique will be used to insert the IV  Treatment of these risks include:  • Removal of IV catheter if subject experiences significant discomfort  • Removal of IV catheter if infection develops
at tips of fingers Potential risks associated with finger stick testing include discomfort and bruising  Risks with IV Catheter Insertion  Risks with IV catheter insertion may include: Pain Bruising Infection Irritation Syncopal episode secondary to catheter insertion Swelling. Discomfort	Prevention and Mitigation  Prevention and mitigation include:  • Qualified individual to perform IV catheter insertion  • Constant observation and monitoring of the subject during FST(s)  • Sterile technique will be used to insert the IV  Treatment of these risks include:  • Removal of IV catheter if subject experiences significant discomfort
at tips of fingers Potential risks associated with finger stick testing include discomfort and bruising  Risks with IV Catheter Insertion  Risks with IV catheter insertion may include: Pain Bruising Infection Irritation Syncopal episode secondary to catheter insertion Swelling. Discomfort Anxiety	Prevention and Mitigation  Prevention and mitigation include:  • Qualified individual to perform IV catheter insertion  • Constant observation and monitoring of the subject during FST(s)  • Sterile technique will be used to insert the IV  Treatment of these risks include:  • Removal of IV catheter if subject experiences significant discomfort  • Removal of IV catheter if infection develops  • Antibiotics will be given, if needed
at tips of fingers Potential risks associated with finger stick testing include discomfort and bruising  Risks with IV Catheter Insertion  Risks with IV catheter insertion may include: Pain Bruising Infection Irritation Syncopal episode secondary to catheter insertion Swelling. Discomfort Anxiety  Risks for indwelling IV catheter	Prevention and Mitigation  Prevention and mitigation include:  • Qualified individual to perform IV catheter insertion  • Constant observation and monitoring of the subject during FST(s)  • Sterile technique will be used to insert the IV  Treatment of these risks include:  • Removal of IV catheter if subject experiences significant discomfort  • Removal of IV catheter if infection develops  • Antibiotics will be given, if needed  Prevention and Mitigation
at tips of fingers  Potential risks associated with finger stick testing include discomfort and bruising  Risks with IV Catheter Insertion  Risks with IV catheter insertion may include:  Pain Bruising Infection Irritation Syncopal episode secondary to catheter insertion Swelling. Discomfort Anxiety  Risks for indwelling IV catheter  Risks with indwelling IV catheters may include:	Prevention and Mitigation  Prevention and mitigation include:  • Qualified individual to perform IV catheter insertion  • Constant observation and monitoring of the subject during FST(s)  • Sterile technique will be used to insert the IV  Treatment of these risks include:  • Removal of IV catheter if subject experiences significant discomfort  • Removal of IV catheter if infection develops  • Antibiotics will be given, if needed  Prevention and Mitigation  Prevention and mitigation include:
at tips of fingers  Potential risks associated with finger stick testing include discomfort and bruising  Risks with IV Catheter Insertion  Risks with IV catheter insertion may include:  Pain Bruising Infection Irritation Syncopal episode secondary to catheter insertion Swelling. Discomfort Anxiety  Risks for indwelling IV catheter  Risks with indwelling IV catheters may include: Infection	Prevention and Mitigation  Prevention and mitigation include:  • Qualified individual to perform IV catheter insertion  • Constant observation and monitoring of the subject during FST(s)  • Sterile technique will be used to insert the IV  Treatment of these risks include:  • Removal of IV catheter if subject experiences significant discomfort  • Removal of IV catheter if infection develops  • Antibiotics will be given, if needed  Prevention and Mitigation
at tips of fingers  Potential risks associated with finger stick testing include discomfort and bruising  Risks with IV Catheter Insertion  Risks with IV catheter insertion may include:  Pain Bruising Infection Irritation Syncopal episode secondary to catheter insertion Swelling. Discomfort Anxiety  Risks for indwelling IV catheter  Risks with indwelling IV catheters may include:	Prevention and Mitigation  Prevention and mitigation include:  • Qualified individual to perform IV catheter insertion  • Constant observation and monitoring of the subject during FST(s)  • Sterile technique will be used to insert the IV  Treatment of these risks include:  • Removal of IV catheter if subject experiences significant discomfort  • Removal of IV catheter if infection develops  • Antibiotics will be given, if needed  Prevention and Mitigation  Prevention and mitigation include:

10976639DOC Version D Page 119 of 170 Medtronic

Thrombosis

Phlebitis

Bruising

	
 
Qualified investigator will be present during experiment
 
Constant observation and monitoring of the subject during FST(s)
 
Observation for redness at IV insertion site by qualified staff
 
Treatment of these risks include:         
 
Removal of IV catheter if infection develops and antibiotics will be given.
 
 
 

Risks with Blood Draw	Prevention and Mitigation

 
Risks with drawing blood may include:
 
Discomfort and bruising
 
Insertion of an IV catheter and drawing blood may also result in faintness, inflammation of the blood vessel, pain and bruising at the needle site
 
There is also a slight possibility of infection.
 
	Prevention and mitigation include:
Risks with IV Saline Infusion	Prevention and Mitigation
Risks with saline infusion may include:	Prevention and mitigation include:  Qualified investigator will be present during experiment  Constant observation and monitoring of the subject during FST(s)  Treatment of these risks include:  Reduction of IV fluid if subject shows signs of congestive heart failure (CHF), lower extremity edema, crackles on lung auscultation or S3 heart sound  Subjects who still exhibit signs of fluid overload at time of discharge will be transported to the emergency room (ER) or follow guidelines of the local institution for the disposition of subject.
Risks with hyperglycemic challenges	Prevention and Mitigation
Risks with hyperglycemia may include:  Diabetic ketoacidosis Symptomatic ketosis Cardiovascular event Dehydration Potassium and sodium imbalance Shock Altered mental status Coma Acidosis	Prevention and Mitigation include:     Follow frequent blood sampling per protocol (See Section 10.2.1.6.4.1 and 11.2.1.6.2.1)     Clear guidelines for management during hyperglycemic challenge     IV access to give immediate insulin     Qualified investigator will be present during experiment     Stopping challenge procedures if ketones are elevated or subject is exhibiting signs and

10976639DOC Version D Page 120 of 170 Medtronic

	symptoms of DKA (Please refer to the ketone management guidelines in the protocol)  Limiting the time the subject is allowed to stay in the hyperglycemic ranges  The subject is under constant observation and monitoring at all times during the challenges  Preventing subjects who do not have a carb/insulin ratio and insulin sensitivity factor from participating in the challenge (observational only)  Investigational centers are to use glucose meter in the event a FST blood glucose value is not available at the required time interval.  Follow the Ketone management instructions per protocol  Treatment of these risks include:  IV fluid administration with normal saline (NS) will be per investigator's discretion  IV insulin administration will be per investigator's discretion  Transfer to ER or follow DKA guidelines of the local institution for the disposition of subject if subject is exhibiting signs and symptoms of DKA
Risks with hypoglycemic challenges Risks for hypoglycemia may include:	Prevention and Mitigation Prevention and Mitigation include:

 
Seizure
 
Coma
 
Altered mental status
 
Loss of consciousness
 
Cardiovascular event
 
Death
 
Risk of rebound hyperglycemia with ketosis
 
	
 
Follow frequent blood sampling per protocol (See Section 10.2.1.6.4.1 and 11.2.1.6.2.1)
 
Clear guidelines for management during hypoglycemic challenge IV access to give immediate dextrose or other emergency drugs
 
Qualified investigator will be present during experiment.
 
Limiting the time the subject is allowed to stay in the hypoglycemic ranges
 
The subject is under constant observation and monitoring at all times during the challenges
 
Preventing subjects who do not have a carb/insulin ratio and insulin sensitivity factor from participating in the challenge (observational only)
 
Investigational centers are to use glucose meter in the event a YSI blood glucose value is not available at the required time interval.
 

10976639DOC Version D Page 121 of 170

Risks with exercise:	Treatment of these risks include:  IV administration of dextrose per investigator's discretion  Glucagon per investigator's discretion  Transfer to ER or follow severe hypoglycemia guidelines of the local institution for the disposition of subject.  Prevention and Mitigation
